8.5.2 Analysis of Secondary Efficacy Endpoints

Summary statistics will be presented for ECHO variables (ventricle size, EF, and SF) and corresponding changes from the study baseline by visit.

All annualized event/duration rate endpoints will be summarized in a similar fashion as for the primary efficacy endpoint.

A data listing of missing visits will be provided for ECHO endpoint by treatment.

8.5.3 Analysis of Exploratory Endpoint(s)

8.5.3.1 SF-10/12

For SF-10 and SF-12, analyses include summary statistics of baseline and change from the study baseline over time for each individual domain and the summary scores. The full analysis set-SF-10 will be used for statistical analyses of SF-10. The full analysis set-SF-12 will be used for statistical analyses of SF-12.

Individual subject listings will be provided for all SF-10/12 tests performed for all subjects in FAS.

A data listing of missing visits will be provided for SF-10 and SF-12v2.

8.5.3.2 Clinical biomarkers endpoints

Biomarker results and corresponding changes from baseline will be summarized descriptively by visit.

8.5.3.3 Growth measurements

Height, weight, and head circumference measurements and the corresponding changes and percent changes from baseline will be summarized descriptively by visit and by age group with summary statistics.

Z-score will be calculated for growth measurements including standing height (or sitting height if applicable) and weight for the male ≤ 18 years, or for the female ≤ 15 years. Z-scores and percentiles will be calculated using (CDC/NCHS) Clinical Growth Charts (Kuczmarski et al. 2000). The plot of height over age with reference to CDC growth chart for each subject will be provided. Data used to produce the United States Growth Charts smoothed percentile curves will be downloaded from the official CDC/NCHS web site: http://www.cdc.gov/growthcharts/percentile_data_files.htm

The data files from the CDC/NCHS that are used for this analysis are summarized below. These files represent the different growth curves for children. LMS refers to the parameters in the CDC Growth Charts Percentile Data Files used to construct the growth curves; these are: the power in the Box-Cox transformation (L); the median (M); and the generalized coefficient of variation (S).

The data files used are:

- Length-for-age charts, birth to 36 months, LMS parameters and selected smoothed recumbent length percentiles in centimeters, by sex and age (LENAGEINF).

- Stature-for-age charts, 2 to 20 years, LMS parameters and selected smoothed stature percentiles in centimeters, by gender and age (STATAGE).

Calculation of Z-scores for length/stature values above and below the median will be performed. Using the CDC/NCHS Clinical Growth Charts, the height-for-age Z score will be calculated using the following equation:

$$Z = \{(X/M)^L - 1\} / (L \times S),$$

where X is the physical measurement (stature in cm) and the LMS parameters are obtained from the appropriate CDC/NCHS Clinical Growth Chart corresponding to the age in months of the child. The percentile corresponding to the Z score is then the corresponding percentile from the standard normal distribution.

For male subjects >18 years and female subjects >15 years, the height and weight will be summarized in centimeter and kilogram respectively.

Weight will be evaluated by z score and percentile using the same method as height based on Centers for Disease Control/National Center for Health Statistics (CDC/NCHS) Clinical Growth Charts (Kuczmarski et al. 2000). The data files used for weight Z-score and percentile are:

- Weight-for-age charts, birth to 36 months, LMS parameters and selected smoothed weight percentiles in kilograms, by sex and age (WTAGEINF).
- Weight-for-age charts, 2 to 20 years, LMS parameters and selected smoothed weight percentiles in kilograms, by sex and age (WTAGE).

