7.5.5.2 Growth and Weight Evaluations

At each clinic visit, measurements of height and weight will be collected for each subject using a stadiometer and a scale. Head circumference will be obtained for subjects \leq 36 months of age. Height, weight, and head circumference (if applicable) data will be used to evaluate each subject's growth using published normative data, when available.

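### SAP 8.5.3.3 admits sitting height into a Z-score that has only recumbent-length and stature references, and gives no rule for choosing the file at 24–36 months

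*SAP*

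**What the plan says.** SAP 8.5.3.3 (Growth measurements) sets the input for the height Z-score: "Z-score will be calculated for growth measurements including standing height (or sitting height if applicable"). It then names two height reference files. The file for the youngest children is given as "Length-for-age charts, birth to 36 months, LMS parameters and selected smoothed recumbent length percentiles in centimeters, by sex and age (LENAGEINF"). The second file, for older children and adolescents, is STATAGE, which holds the CDC norms for stature by age from 2 to 20 years.

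The equation is Z = {(X/M)^L − 1}/(L × S). Its terms are explained in this way: "where X is the physical measurement (stature in cm) and the LMS parameters are obtained from the appropriate CDC/NCHS Clinical Growth Chart", matched to the child's age in months. A neighbouring sentence refers to length and stature values together. No sitting-height reference, conversion or exclusion appears. SAP 8.5.5.3 reuses the method for the integrated growth analysis of the CL201 rollover cohort.

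On measurement, protocol 7.5.5.2 says that "measurements of height and weight will be collected for each subject using a stadiometer and a scale" at each clinic visit; it gives no measuring position. Protocol Table 2.1 (footnote 5) and the matching SAP schedule list height and weight, plus head circumference up to 36 months. Neither has a separate item for recumbent length or sitting height. Enrolment starts at 6 months of age (protocol 7.3.1).

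On head circumference, the same protocol section says, alongside the other growth measures, that "head circumference (if applicable) data will be used to evaluate each subject's growth using published normative data", qualified to cases where such norms exist. SAP 8.5.3.3 summarises head circumference as values, changes and percent changes. The reference files named there cover only length, stature and weight.

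**The concern.** A Z-score is valid only if the measurement is of the same kind as the reference. Sitting height is a different body dimension from stature and from recumbent length, and neither named file is a norm for it. The input sentence therefore conflicts with the section's own definition of X. A programmer who follows the sentence would put a sitting height into the stature equation and obtain a number with no meaning.

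The second gap is in file selection. The chart is chosen by age, but both files are valid from 24 to 36 months. In that band the answer depends on whether the child was lying or standing, and the SAP does not use that information. A child may stay in the study for up to 84 months, so one enrolled young can pass through the band. If the file changes there while the measuring position does not, or the reverse, part of the change in Z is artefact.

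Growth is an exploratory endpoint and a general assessment in a study that enrols young children and targets 25–35% of calories from study drug, so the height Z-scores will be read with some interest.

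**Working it through.** The documents give no Z-score, LMS value or expected count of affected children, so there is no figure of the plan's to reproduce. The check applies the SAP's own equation to a child whose true value equals the median, for whom the correct answer is Z = 0.

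**Inputs.** From SAP 8.5.3.3: the equation, the two files and their age ranges. Assumed, because the documents do not give them:

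- sitting height 0.50–0.65 of stature
- S = 0.035–0.05
- L = 1 (varied from -1 to 2 as a sensitivity check)
- standing height 0.5–1.0 cm below recumbent length
- for young children, M = 68–95 cm with S = 0.035–0.045

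**Sitting height scored on the stature file.** With L = 1 the equation becomes Z = (X/M − 1)/S.

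| X/M | S = 0.035 | S = 0.04 | S = 0.045 | S = 0.05 |
|---|---|---|---|---|
| 0.50 | -14.3 | -12.5 | -11.1 | -10.0 |
| 0.55 | -12.9 | -11.2 | -10.0 | -9.0 |
| 0.60 | -11.4 | -10.0 | -8.9 | -8.0 |
| 0.65 | -10.0 | -8.8 | -7.8 | -7.0 |

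For example, (0.65 − 1)/0.05 = -7.0 and (0.50 − 1)/0.035 = -14.3. Letting L run from -1 to 2 widens the range to -5.8 to -28.6.

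Break-even: for Z to stay at or above -2 with L = 1, X/M must be at least 1 − 2S, which is 0.93 at S = 0.035 and 0.90 at S = 0.05. The assumed ratios are far below that.

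**Standing height scored on the length file.** With L = 1, Z = −d/(M × S), where d is the gap in cm.

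- M = 95, S = 0.045, d = 0.5: −0.5/4.275 = -0.12
- M = 85, S = 0.035, d = 1.0: −1.0/2.975 = -0.34
- M = 68, S = 0.035, d = 1.0: −1.0/2.38 = -0.42

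The error is about 0.1–0.3 at the larger medians and reaches 0.4 at the smallest one tried, so 0.1–0.4 is a cautious outer range for 24–36 months. The reverse mismatch (a recumbent length scored as stature) has the opposite sign. With d = 0, or with position and file matched, the error is zero.

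**The case against.** The strongest reply is that the harm is conditional. Sitting height is not a scheduled item in either document, and the SAP's qualifier may describe no child at all. Nothing indicates how often it would be used. Protocol 7.5.1 and 7.5.5 also send the reader to a Study Reference Manual, which is not among the documents and may fix measuring technique by age. All this stands as a limit on the size of the problem. It does not repair the sentence, which admits the value without providing a reference for it.

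A reader might infer that infants are being scored as standing or sitting children against a lying-length norm, because the protocol mentions a stadiometer and the SAP never lists recumbent length as an input. The documents do not support that. The SAP sends birth to 36 months to the recumbent-length file and speaks of length as well as stature. The protocol states no position, and a 6-month-old cannot give a standing height. If infants were measured lying, their error is zero.

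A reader might also infer that false severe short stature or false growth failure would enter the conclusions. That is too strong. Growth is summarised descriptively, and SAP 8.5.4.3 does not list it among the tested endpoints. Raw heights and individual plots against the CDC chart are also planned, and SAP 7.1 provides for querying questionable data. A value of -7 or lower would probably be noticed. The 24–36 month error is less conspicuous but also much smaller.

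On head circumference, the protocol's commitment is qualified, and SAP section 1 gives the SAP precedence on analysis. The gap is real but secondary.

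**Conclusion.** The point holds, at minor severity. As written, SAP 8.5.3.3 contradicts itself: it allows sitting height into a Z-score whose only references are recumbent length and stature and whose X is stature. Any sitting height so scored would be invalid, by roughly -7 to -14 for a median child. That size rests on the assumed ratio, S and L, but no value in the assumed ranges brings the result near a usable score. Separately, the file is undetermined at 24–36 months, and a mismatch of position and file would cost about 0.1–0.4 in Z under the assumed gap of 0.5–1.0 cm.

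How many children either problem touches cannot be determined from the documents. The consequences stay within the height Z-scores and percentiles, including those in the CL201 rollover growth analysis. Raw heights and the major clinical event endpoints are not affected.

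**What to change.** In SAP 8.5.3.3:

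1. Delete the sitting-height alternative from the Z-score input and show any sitting heights in a listing only.
2. Define X as recumbent length or stature, in cm.
3. Score recumbent length on LENAGEINF and standing height on STATAGE. At 24–36 months choose the file by the recorded measuring position; where position was not recorded, use one fixed file for the whole band and say so in the table footnote.
4. Optionally, add a head-circumference-for-age Z-score for subjects up to 36 months, where a published reference is available, to match protocol 7.5.5.2.

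The cost is SAP wording and a small programming change, plus one extra reference file if item 4 is adopted. A few sitting-height values, if any exist, leave the Z-score table. A new measuring instruction to sites would not be enough, because SAP version 2.0 is dated 21 December 2020 and an instruction cannot classify measurements already taken. Item 3 therefore needs its fallback. Under the fallback a shift of a few tenths in Z may remain for some children, but the rule would be stated and the same for everyone.

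### Height and weight Z-scores stop at 15 in girls and 18 in boys although the SAP's own reference files run to 20, and head circumference has no reference-based analysis

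*SAP*

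**What the plan says.** SAP 8.5.3.3 sets three rules for growth.

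- Z-scores and percentiles are calculated for height and "weight for the male ≤ 18 years, or for the female ≤ 15 years". Beyond those ages, "For male subjects >18 years and female subjects >15 years, the height and weight will be summarized in centimeter and kilogram respectively". No reason is given for the limits, or for their differing by sex.
- The reference files for older children are "Stature-for-age charts, 2 to 20 years, LMS parameters and selected smoothed stature percentiles in centimeters" and "Weight-for-age charts, 2 to 20 years, LMS parameters and selected smoothed weight percentiles in kilograms", both by sex. Separate infant files cover birth to 36 months for length and weight.
- Height, weight and head circumference are also summarised as raw value, change and percent change, by visit and age group. In addition, "The plot of height over age with reference to CDC growth chart for each subject will be provided". No age limit is attached to that plot, and no matching plot is planned for weight.

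No head-circumference reference file or Z-score formula is listed.

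Protocol 7.5.5.2 says that height, weight and, where applicable, head circumference will be used to evaluate each subject's "growth using published normative data, when available". The protocol synopsis likewise promises a comparison with normal growth rates for paediatric and adolescent subjects. SAP section 1 gives the SAP precedence over the protocol on analysis.

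**The concern.** The plan names references that run to 20 years and then stops using them earlier, three years sooner in girls than in boys. The SAP treats subjects under 18 as paediatric (summary of changes, item g). A girl between 15 and 18 is therefore a paediatric subject, inside the reference, and unscored. Her raw weight change mixes ordinary adolescent growth with whatever treatment does. If the unstated reason is that girls are near final height by 15, it would not justify stopping weight as well.

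Weight deserves a proper scale here. The product supplies a target of 25-35% of calories, and protocol 5.2.3 describes the evidence against excess weight gain as anecdotal.

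Head circumference has the same problem in sharper form. In children up to 36 months the raw value rises with normal growth, so raw change cannot by itself separate slowed growth from normal growth.

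**Working it through.** The documents state no derived figure for growth, so there is nothing to reproduce. The check is age arithmetic.

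**Inputs.** The limits are 15 (girls) and 18 (boys), and the files end at 20 (SAP 8.5.3.3). Follow-up F is at most 7 years and ends earlier on market approval (SAP 3.3). Growth is measured at six-monthly clinic visits (SAP 11.5). Minimum entry age is 0.5 years (protocol 7.3.1).

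**Assumptions.** Entry age is uniform from 0.5 to 18 years in each sex, because the documents give no distribution. The limit is first applied to age at visit. Everyone is followed for the full F years.

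**Formula.** An entrant aged a has max(0, min(F, L − a)) years of scored follow-up under an age limit L. Summing over entry ages gives areas, of which only the ratios matter.

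| F | Girls, L = 15 | Boys, L = 18 | Files, L = 20 |
|---|---|---|---|
| 1.5 y | 1.5×13 + 1.5²/2 = 20.625 | 1.5×16 + 1.5²/2 = 25.125 | 1.5×17.5 = 26.25 |
| 7 y | 7×7.5 + 7²/2 = 77 | 7×10.5 + 7²/2 = 98 | 7×12.5 + (7² − 2²)/2 = 110 |

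**Share of file-covered follow-up left unscored.**
- Girls: 1 − 20.625/26.25 = 21% at 1.5 years; 1 − 77/110 = 30% at 7 years.
- Boys: 1 − 25.125/26.25 = 4% at 1.5 years; 1 − 98/110 = 11% at 7 years.

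A direct count of six-monthly visits gives the same rounded values.

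**Below 18 only.** The boys' column becomes the denominator.
- Girls: 1 − 20.625/25.125 = 18% at 1.5 years; 1 − 77/98 = 21% at 7 years.
- Boys: 0% throughout.

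**Sensitivity to entry age.** The share of girls' visits below 18 left unscored, by visit count, is:
- entry at 0.5-6 years: 0%;
- entry at 6-12 years: 0% (3-year follow-up) to 19% (7-year);
- entry at 12-18 years: 67% (3-year) to 73% (7-year).

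**Age at enrolment instead.** SAP 5.13 derives age from the consent date unless otherwise specified. On that reading, with the same entry ages, 3/17.5 = 17% of girls (those entering above 15) are never scored, and no boy is affected. Everyone else stays eligible throughout. That reading runs off the end of the files, however. A girl entering at 15 would be 22 after 7 years and a boy entering at 18 would be 25, both past 20.

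**Composition of by-visit means, age at visit.** The proportion scored changes between baseline and Month 84 as follows:
- girls: from 14.5/17.5 = 83% to 7.5/17.5 = 43%;
- boys: from 100% to 10.5/17.5 = 60%;
- either sex with a limit of 20: from 100% to 12.5/17.5 = 71%.

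Extending the limit reduces the change in composition and makes it equal in the two sexes, but does not remove it.

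**Head circumference.** No arithmetic is needed for the main point: the protocol names it among the measures to be judged against normative data, and the SAP lists neither a file nor a method. Under the same assumption, 2.5/17.5 = 14% of entrants below 18 would be 3 years or younger at entry.

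**The case against.** The strongest reply is that little is actually missing. Height and weight above the limits are still summarised by visit and age group. Raw data are listed (SAP 8.1), so Z-scores could be derived later, and each subject has a height plot against the CDC chart. Clinically significant weight changes are recorded as adverse events (protocol 7.5.5.7). All of this stands. A reader might infer that long-term growth data are lost; they are not. What is missing is the age-standardised summary and, for weight, any reference at all.

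A reader might also infer that many paediatric subjects are affected. The documents do not support that. Boys are scored throughout the SAP's paediatric range, so the age-limit gap below 18 is confined to girls over 15, and their number is unknown.

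It is tempting to assume entry ages of 0.5 to 15 and 7 years for everyone. Then 7/14.5 = 48% of girls leave the series before Month 84, and 1 − 5.31/6.86 = 23% of scorable time goes. That arithmetic is right, but it uses the ceiling on follow-up and takes age at visit as settled. With 3 years the figures are 3/14.5 = 21% and 1 − 39/43.5 = 10%. If the consent-age default governs, nobody leaves mid-study because of the limit.

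Nor is it certain that by-visit mean Z-scores drift. They shift only if those who leave differ in Z-score from those who stay.

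On head circumference, the protocol's commitment is conditional on normative data being available, and the SAP takes precedence. The word 'including' in the SAP's Z-score sentence could be stretched to cover head circumference, but nothing listed would support the calculation. Summaries by age group reduce the confounding with normal growth only in part.

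Finally, growth is exploratory and descriptive, and no primary or secondary result rests on it. In a single-arm study, Z-scores would not isolate a drug effect either; they would remove expected growth for age and sex. That limits the weight of the point without answering it.

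**Conclusion.** The point holds as a minor one. The Z-score limits are narrower than the SAP's own references, unexplained and unequal by sex. Below 18 they leave girls over 15 without any reference-based weight analysis. Head circumference falls short of the comparison described in protocol 7.5.5.2.

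The loss of 21% to 30% of scorable visits in girls and 4% to 11% in boys rests on uniform entry ages from 0.5 to 18 and on age at visit; the boys' loss lies wholly above 18. For girls' visits below 18 the share could be anywhere from 0% to about 73%, depending on entry age and follow-up. The girls' gap persists if the study ends early, because under this assumption those entering above 15 are never scored. If the limit means age at enrolment, only girls entering above 15 and boys entering above 18 are unscored. A shift in by-visit mean Z-scores is possible under age at visit, not established.

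**What to change.** Amend SAP 8.5.3.3 in three places.

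1. Calculate height and weight Z-scores and percentiles for both sexes at every visit, by age at that visit, up to the 20-year end of STATAGE and WTAGE. If the 15 and 18 limits are kept, give the reason and state which age they refer to. The integrated rollover analysis (SAP 8.5.5.3) adopts the same method and would follow.
2. Name a published head-circumference-for-age reference and add a Z-score for subjects up to 36 months.
3. Keep the existing raw summaries, which remain the right display beyond 20 years.

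The cost is one age condition in the program and one further reference file, which the SAP has to identify because the documents name none. No extra data collection is needed. Report the number scored, by sex, beside each by-visit mean, because some subjects will still pass 20 during follow-up.

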7.3.1 Inclusion Criteria

Individuals eligible to participate in this study must meet all of the following criteria:

- 1. Male or female, 6 months of age or older
- 2. Prior participation in a clinical study assessing UX007/triheptanoin treatment for LC-FAOD. Study Sponsors/Collaborators include: Oregon Health & Science University, University of Pittsburgh, and Ultragenyx Pharmaceutical (ClinicalTrials.gov Identifiers: NCT01379625, NCT01461304, and NCT01886378). Patients who received UX007/triheptanoin treatment as part of other clinical studies; investigator sponsored trials (IST); expanded access/compassionate use treatment programs; or patients who are treatment naïve (i.e., naïve to both UX007 and food-grade triheptanoin), have failed conventional therapy and, in the opinion of the Investigator and Sponsor, have documented clear unmet need, may also be eligible at the discretion of the Sponsor.
- 3. Confirmed diagnosis of LC-FAOD including: carnitine palmitoyltransferase (CPT I or CPT II) deficiency, very long chain acyl-CoA dehydrogenase (VLCAD) deficiency, long chain 3-hydroxy-acyl-CoA dehydrogenase (LCHAD) deficiency, trifunctional protein (TFP) deficiency, or carnitine-acylcarnitine translocase (CACT) deficiency. Information

on diagnosis will be obtained from medical records and should include confirmed diagnosis by results of acylcarnitine profiles, fatty acid oxidation probe studies in cultured fibroblasts, and/or mutation analysis.

- 4. Willing and able to complete all aspects of the study through the end of the study, including visits and tests, documentation of symptoms and diet, and administration of study medications. If a minor, have a caregiver(s) willing and able to assist in all applicable study requirements.
- 5. Provide written informed consent (subjects aged ≥ 18 years), or provide written assent (where appropriate) and have a legally authorized representative willing and able to provide written informed consent, after the nature of the study has been explained and prior to any research-related procedures.

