5.13 Age at Enrollment

Unless otherwise specified, the age will be derived based on the informed consent date in CL202: Age = (Inform Consent Date (ICF) – Birth Date +1)/365.25. The age will be rounded down to the nearest years and kept to one (1) decimal place. When date of birth is missing, the age recorded on CRF will be used.

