8.4.3 Demographic and Baseline Characteristics

Summary statistics will be presented for the Full Analysis Set and by subgroup for the following (but not restricted) parameters

- Gender

- Ethnicity
- Race
- Gestational age at birth
- Age at enrollment (ICF date)
- Age at LC-FAOD diagnosis
- Age at first dose of UX007 (in CL202)
- Age at first dose of UX007 (only for CL201 rollover subjects and UX007/trihep naïve subjects)
- Height at baseline
- Weight at baseline
- BMI at baseline

As only limited demographics data (i.e., date of birth and sex) and LC-FAOD diagnosis and LC-FAOD medical history are entered into the clinical database for subjects who previously participated in the UX007-CL001 or UX007-CL201 study, the UX007-CL001 and UX007-CL201 databases will be integrated with UX007-CL202 database to obtain complete data on demographics , LC-FAOD diagnosis, and LC-FAOD medical history.

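### Infant growth Z-scores have no correction for preterm birth, so preterm-born subjects under about 2 years at baseline can show an upward drift that is not real growth

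*SAP*

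**What the plan says.** SAP 8.5.3.3 computes height Z-scores by the LMS formula, Z = {(X/M)^L - 1}/(L x S). On the choice of reference values it states: "the LMS parameters are obtained from the appropriate CDC/NCHS Clinical Growth Chart corresponding to the age in months of the child". The same section adds: "Weight will be evaluated by z score and percentile using the same method as height". It names CDC infant files covering birth to 36 months for both measures. SAP 8.5.5.3 applies the same method to CL201 rollover subjects, measured from the UX007 treatment baseline.

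The section does not define the age in months. The only explicit age formula in the SAP is in 5.13, for age at enrollment: "Age = (Inform Consent Date (ICF) – Birth Date +1)/365.25". It counts from the date of birth.

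SAP 8.4.3 lists "Gestational age at birth" among the baseline characteristics. Neither document uses it anywhere else, and neither mentions corrected age.

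Infants can be enrolled. Protocol 7.3.1 sets the lower limit as "Male or female, 6 months of age or older". Protocol 7.4.4 has a dietary-analysis rule for patients under 1 year, and SAP 8.7.1 plans an adverse-event age category of 0-1 year.

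**The concern.** A child born several weeks early and scored at chronological age is compared with children who have had more growing time since conception. The lag is fixed in weeks. Its size in SD units shrinks as growth slows and the spread of the reference population widens. The Z-score therefore starts too low and climbs even if the child follows the reference curve exactly.

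The study has no control arm to show the same climb without UX007. The plan also gives growth a role in describing the drug's effect. The rationale for Protocol Amendment 5 includes growth among the exploratory endpoints meant to characterize a possible treatment effect. SAP 8.5.5 assesses long-term effects in rollover subjects partly through non-MCE parameters, and 8.5.5.3 names only two: echocardiography and growth. Growth also appears among the safety and general assessments in the protocol. A built-in rise could thus look like benefit, or could offset and hide a real decline.

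**Working it through.** **Inputs.** The documents give no LMS values, no count of infants or preterm-born subjects, and no figure to reproduce. From the SAP come the Z formula and the conversion of 30.4375 days per month (5.5). All growth values below are assumptions, not CDC values. The child is assumed to lie on the median for corrected age.

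**Check 1: velocity and SD.** With L = 1 the SAP formula becomes Z = (X - M)/(M x S), the distance from the median in SD units. A child with a lag of c months falls short by about c x velocity, so:

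Z error = c x velocity / SD, with c = weeks early x 7/30.4375.

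Assumed length velocity and SD:
- near 6 months: 1.4-1.8 cm/month, SD 2.4-2.6 cm
- near 24 months: 0.8-1.0 cm/month, SD 3.2-3.5 cm

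Six weeks early: c = 42/30.4375 = 1.38 months.
- At 6 months: 1.38 x 1.4/2.6 = 0.74 to 1.38 x 1.8/2.4 = 1.03 SD too low.
- At 24 months: 1.38 x 0.8/3.5 = 0.32 to 1.38 x 1.0/3.2 = 0.43 SD too low.
- Apparent gain, full range: 0.74 - 0.43 = 0.31 to 1.03 - 0.32 = 0.71 SD.

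The same steps for other degrees of prematurity:

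| Weeks early | Deficit at 6 months | Deficit at 24 months | Apparent gain |
|---|---|---|---|
| 4 | 0.50-0.69 | 0.21-0.29 | 0.21-0.48 |
| 6 | 0.74-1.03 | 0.32-0.43 | 0.31-0.71 |
| 8 | 0.99-1.38 | 0.42-0.57 | 0.42-0.96 |

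**Check 2: a different assumed curve.** Take M(a) = 50 + B x sqrt(a) cm with B from 6.5 to 8, S from 0.033 to 0.041 and L = 1. Set X = M(a - c) and score at age a.

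| Months early | Z at 6 months | Z at 24 months | Drift 6-24 | Drift 12-24 | Drift 24-36 |
|---|---|---|---|---|---|
| 1 | -0.74 to -0.51 | -0.28 to -0.20 | 0.31-0.46 | 0.12-0.18 | 0.05-0.07 |
| 2 | -1.57 to -1.08 | -0.57 to -0.40 | 0.68-1.00 | 0.26-0.37 | 0.10-0.15 |

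Scored at corrected age, the same child has Z = 0 at every visit and no drift. The two checks agree on direction and broadly on size. The drift is largest from a baseline near 6 months, smaller from 12 months, and small from 24 months. Some deficit is still present at 24 months and later.

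**Effect on a group mean.** Shift = share of Z-scored subjects affected x drift. The share is not stated. At an assumed 2-10% and a drift of 0.3-1.0, the mean moves by 0.02 x 0.3 = 0.006 to 0.10 x 1.0 = 0.10. At 20% it moves by 0.06 to 0.20. A summary of the youngest age group would show more.

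Only length was sized. For weight, the direction is the same wherever weight gain slows with age.

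**The case against.** Several points on the other side stand.

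- **Z-score change is not expressly planned.** SAP 8.5.3.3 attaches change and percent change from baseline to the measurements themselves, and Table 11.1.1 lists height, weight and head circumference. Changes in cm or kg do not depend on the reference age. The drift appears only when Z-scores or percentiles are compared across visits. Since the SAP calculates both for growth, that comparison is an obvious one to make.
- **Chronological age is inferred.** The formula in SAP 5.13 covers enrollment only, and 8.5.3.3 does not say which age it means. A reader might infer that the SAP mandates uncorrected age. It does not; it is silent, and a programmer would most naturally count from the birth date.
- **A reader might infer that the study would credit the drift to UX007.** The documents do not support that. Growth is exploratory and descriptive, is not among the endpoints tested in SAP 8.5.4.3, and carries no planned claim. What remains is that a single-arm design could not separate the drift from a treatment effect if someone interpreted it.
- **Few subjects may be affected.** Protocol 7.3 expects most subjects to have had prior exposure, so CL202 baseline is often not a pre-treatment value. Rollovers who completed the 78 weeks of CL201 are at least about 18 months old at CL202 baseline (78 x 7/30.4375 = 17.9), which removes the largest drift from their CL202 change. They could still be affected in the integrated analysis, but CL201's minimum entry age is not given.
- **Partial safeguards exist.** Summaries by age group and individual height plots against the CDC chart help a reader notice an odd pattern. They do not remove it.

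**Conclusion.** The point holds as a minor analysis choice that should be changed. Read in the natural way, the plan scores preterm-born infants too low and builds in an upward Z-score trend for those under about 2 years at baseline. For birth 6 weeks early, the apparent length gain from 6 to 24 months is roughly 0.3 to 0.7 SD. That rests on assumed velocities and SDs and on a child tracking the median for corrected age.

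A reader might infer that only measurements before 24 months are affected. That is too narrow: the assumed figures leave 0.32-0.43 SD of error at 24 months, which decays afterwards.

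The effect on any group mean depends on a share of subjects that the documents do not give. The primary and secondary endpoints are not affected.

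**What to change.** Add to SAP 8.5.3.3, and carry into 8.5.5.3:

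- For subjects born before 37 weeks whose baseline falls under 24 months of age, compute Z-scores and percentiles at corrected age: chronological age minus (40 weeks minus gestational age). Baseline means the study baseline, or the UX007 treatment baseline in 8.5.5.3.
- Keep that age basis for the subject's baseline and all later visits in the Z-score trend. Reverting to chronological age at 24 months would create an artificial drop of about 0.32-0.43 SD at 6 weeks early (0.42-0.57 at 8 weeks).
- Show the chronological-age Z-scores alongside.
- Report how many subjects were corrected and how many had missing gestational age.

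The 37-week, 40-week and 24-month values are not in the documents. They are proposed conventions to fix before the Z-scores are examined.

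The cost is a short rule, one derived age variable and one extra display. Subjects with missing gestational age stay uncorrected. That may matter, because SAP 8.4.3 lists the variable but the demographics in Protocol 7.5.5.1 do not. Subjects aged 24 months or more at baseline also stay uncorrected, with a drift from 24 to 36 months of about 0.05-0.15 SD if born 1 to 2 months early, under the second set of assumptions.
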